10.6 Intervention

Participants will receive one of the following influenza vaccines: AD influenza vaccination (Southern Hemisphere formulation, FLUAD[®] Quad (Influenza Vaccine, Adjuvanted), quadrivalent, Seqirus) or nonadjuvanted SD influenza vaccination (Southern Hemisphere formulation, Sanofi Pasteur) (Appendix G). Immediately after vaccination, participants will be asked to remain in observation by a nurse and a physician at the clinical site for a short period of approximately 30 minutes.

10.6.1 Vaccine Storage and Handling

The vaccines will be stored at each site, refrigerated at 2 °C to 8 °C. Before the administration, the prefilled syringe or vial has to be shaken. Opened and used vials are not to be reused and they will be identified with the

subject ID number and stored at room temperature at the study clinic for the study monitors to review, and later stored at the site until destroyed at the end of the study. Remained unused vials from 2-8°C freezer must NOT be used. At the end of the study, after being reconciled and upon consent by CDC and in coordination with the Peruvian DIGEMID, the used and opened vials will be destroyed.

10.6.2 Vaccine Preparation

On Study Day 0, the investigational nurse or designee will be provided with applicable information for each eligible subject. The investigational nurse or designee will use the randomization list provided by the randomization software in which will indicate the vaccine assignment and the respective randomization code number. The investigational nurse will assign the vaccine to the next available subject. For each subject randomized, the investigational nurse or designee at the time of the vaccination will prepare the vaccine according to instructions that will be provided separately and a label bearing the study subject's identification number, subject's initials, date and randomization code number. After filling in the data, the study nurse will place a transparent sticker covering the label on the syringe, to ensure the preservation of the information.The used vial will be stored at room temperature.

The subject's identification number, initials and randomization code number will be transcribed onto the Vaccine Administration Log.

10.6.3 Vaccine Administration

All vaccines products are to be administered under the supervision of the Principal Investigator or a qualified sub investigator physician designated to CDC in writing prior to the trial and trained in both the protocol and contents of the Investigators' Brochure. Under no circumstances will the Principal Investigator allow investigational products to be used other than as directed by this protocol.

On day 0, before vaccination, subjects will provide approximately 10 mL of venous blood (*pre-vaccination specimen*, Appendix F).

Vaccine will be prepared as described in 10.6.2 and administered after removal from the freezer.

Administrations of the vaccine will be given by intramuscular injection into the deltoid muscle region on Day 0. The vaccination will be given into the non-dominant arm of each subject. Each site should be wiped with an alcohol wipe before injection of the vaccine. The arm used (right or left) and the time when the vaccination was given should be recorded in the CRF and source document.

10.6.4 Post-Vaccination

Emergency equipment will be available on site and procedures instituted in the event of anaphylaxis post vaccination. Medical personnel will be on site for investigational product vaccination and remain at least +30 minutes after administration of the vaccine to the last subject on the day of vaccination. The following procedures and assessments will be performed and results recorded on the subject CRF:

- Vital signs including Heart Rate, Blood Pressure, Respiratory Rate, and temperature
- If indicated by a change in subject health status, an optional targeted physical examination including HEENT, heart, lungs, abdomen, skin, neurological, and musculoskeletal systems may be performed at the discretion of the Investigator.
- Perform vaccination symptom assessment

- Subjects will be queried regarding the occurrence of AEs since administration of study vaccine
- Subject will be asked about their current state of health and be reminded to capture signs and symptoms in the memory aid (Appendix U)
- Subjects will be informed that an auxiliary study nurse will contact them by phone to set a visit on Day 3 (+ 2) and Day 7(+ 2) to conduct a safety assessment. However, due to pandemic, if for any reason the participant have some impediment in attending the venue in person; it would be possible to set up a virtual visit.
- Further assessments that need to be performed will be recorded on the "Unscheduled CRF(s)".
- A vaccination study card will be provided with the date of the vaccination.
- The time of completion of evaluation and time of discharge will be recorded.

10.7 Follow up

Study staff will contact participants on day 3 (Appendix H) and day 7 (Appendix I) to ask about potential adverse effects or reactions participants might have developed after vaccination.

On day 28 (range 21-35 days), participants will provide another 10 ml sample of whole blood (*post-vaccination specimen*, Appendix F).

At the end of the influenza season, participants will provide a final sample of whole blood (10 ml) (*end of season specimen*, Appendix F) and complete an end of season questionnaire (Appendix J).

10.7.1 End of Season Survey

A brief telephone survey (or in person, if needed, as last method of data collection after internet and telephone) administered at the end of the influenza season will provide a final opportunity to report the occurrence of previously unreported illnesses (especially medically attended illnesses), and the possible use of prophylactic medications that were not reported during surveillance. Brief updates on participants' health status and other infection control and preventive measures may also be included as well as an infection control.

10.8 Surveillance monitoring

An *acute illness¹* is defined as one or more of the following symptoms within the past 7 days: cough, runny nose, body aches, or feverishness (could be not measured fever). The focus of the study is on acute or newly worsened symptoms; this will be emphasized in the phrasing of screening questions, orientation to

¹Sources for this method and similar items can be found in the following manuscripts:

Irving et al. (2011) Comparison of clinical features and outcomes of medically attended influenza A and influenza B in a defined population over four seasons: 2004–2005 through 2007–2008. Influenza and Other Respiratory Viruses DOI: 10.1111/j.1750-2659.2011.00263.x

participants, and staff training. Nonetheless, participants will be discouraged from assuming they know the source of symptoms or dismissing symptoms they might attribute to allergies or non-infectious sources, since the study intends to assess all acute illnesses regardless of presumed etiology. Following are active surveillance steps.

- a. Starting at enrollment, reports of acute illness pre-season will be acknowledged by study staff but will not prompt respiratory specimen collection;
- b. During the approximately 10-20 weeks of local influenza circulation, participants will receive twiceweekly communication via cellphone messaging (e.g. *WhatsApp*) or phone call to confirm whether they have acute illness symptoms;
- c. During follow up participants will be asked to contact study staff immediately by cellphone messaging (e.g. *WhatsApp*) or telephone when they experience symptoms of acute illness; when possible, some facilities will check staff schedules to identify participants who might have missed work because of illness in order to proactively contact them;
- d. Participant reports of symptoms will be logged by study staff in a "Symptom Screening Log" (Appendix K);
- e. Participants who report an acute illness (within 7 days of illness onset) will be asked to self-collect a respiratory specimen; a nasal swab will be collected using kits provided by study staff [25-27]. If the participant does not wish to self-swab, study staff will perform the nasal swab through a visit to the participant's workplace or home (Appendix L);
- f. Participants who self-swab will either hand deliver their specimen to the study staff located at their facility or contact study staff (by telephone or SMS) for pickup within 24 hours of swabbing whenever possible (but no later than within 72 hours);
- g. Participants will complete staff-administered telephone (or in person, if needed, as secondary method of data collection after trying telephone contact) acute (Appendix M) and follow-up interviews (Appendix N);
- h. Participants will return to active surveillance at illness resolution (reporting at least one day without symptoms) or two weeks post-illness onset, whichever comes first;

10.8.1 Symptom Screening Log

During study orientation and as part of obtaining informed consent, study staff will emphasize that the study is interested in even mild or minor illnesses. Although each individual has somewhat different definitions of feeling "sick" or "ill," orientation will encourage participants to consider even mild feelings of this nature as constituting feeling sick or ill. Participants will be encouraged to respond to twice-weekly SMS messages to confirm if they are sick with an acute illness. Participants who do not response to SMS will be called on the telephone by study staff. If participants report an acute illness during the active surveillance period by SMS message or direct contact to study staff (as described below), study staff will assess illness symptoms and onset date using the Symptom Screening Log (Appendix K).

10.8.2 Acute Illness Survey

Participants with qualifying acute illnesses that trigger respiratory specimen collection (see below) will be asked questions about their illness through an Acute Illness Survey (Appendix M). The survey items will be administered by study staff by telephone (or in person, if needed, as secondary method of data collection after trying telephone contact) and include date of illness onset, symptoms and subjective severity, missed work and perceived productivity, patient contact and precautions taken to avoid transmission, receipt of medical care, and use of antiviral or antibiotic prescriptions.

10.8.3 Illness Follow-up Texts and Survey

Seven days after the illness onset date, participants will be sent a message to their mobile phone asking if their illness has been resolved. An illness episode will be considered to have been resolved when the participant subjectively reports he or she is "no longer sick." If the illness has not been resolved, inquiries will be repeated every 48 hours until the illness is resolved or up to 3 contacts (or on days 9, 11, and 13 post illness onset). If symptoms have become worse or a new symptom is added on day 13, a new episode will be considered and steps in section 9.8 will apply.

Regardless of illness resolution, participants will be telephoned approximately 10 days after the illness onset date and asked to complete a brief Illness Follow-up Survey (Appendix N), which addresses symptoms, missed work, productivity, and medical care for the days since completion of the Acute Illness Interview.

10.8.4 Timing of Active Surveillance

We will refer to historical patterns for the start and end of local influenza circulation in planning study milestones. We will also monitor all available sources (e.g. NAMRU-6 influenza surveillance, INS-MOH) of local surveillance for laboratory-confirmed influenza virus infections, allowing for starting surveillance up to two-four weeks prior to typical influenza circulation. Participants will be prompted to begin active surveillance for acute illnesses as soon as US CDC and the study site PI confirm that seasonal influenza is circulating locally or there are indicators that circulation is imminent. Participants will also be notified when local influenza circulation or the season has ended via SMS message, an email, or a telephone call, based on the same epidemiological data used to trigger the start of the season.

10.9 Masking (blinding)

The principal investigators will be in charge of the blinding. This will be a double-blind study, meaning that the participant will be unaware of the type of influenza vaccination that he/she will receive and study staff and serologic tests will be blinded to vaccine type/dose.

10.9.1. Blind opening contingency plan Masking (blinding)

Only in the event of an emergency or serious adverse event or other particular event that alters the riskbenefit profile of the intervention will the principal investigator determine whether unmasking of a participant's study intervention assignment is justified. The safety of the participants should always be the first consideration when making such a determination. If the investigator decides that opening the blind is warranted, the investigator should make every effort to communicate such a decision by telephone or mail to the sponsor or medical monitor prior to unmasking a participant's treatment assignment, unless this can delay the process of opening the participant's assignment, since it is necessary to have the approval of one of them in order to be able to communicate with the person responsible for the randomization, who has access to the central randomization lists by Code of each participant, and thus request such information.

The date and reason why the blind was broken must be recorded in the source documents and in the CRFe by the investigator of the research center.

If the treatment allocation blind is opened, this information should only be shared with the other medical researchers of the center when it is necessary to know it (especially when the cause is a safety event that corresponds to a serious adverse reaction). Information about treatment allocation should not be shared with other people.

10.10 Withdrawal of Subjects from the Study

Every reasonable effort should be made to ensure that each subject complies with the protocol and completes all study visits. However, a subject may voluntarily withdraw or be withdrawn involuntarily from participation if:

- The subject withdraws consent.
- The investigator recommends discontinuation in the interest of the subject's safety (i.e., adverse event related) or because of significant and irremediable protocol non-compliance.
- CDC, NAMRU6, the IRB terminates the clinical trial for safety or other reasons.

Any adverse event leading to early discontinuation will be followed to resolution. No subject prematurely withdrawing/withdrawn will be replaced.

10.11 Halting Rules

The study will be halted for safety review by the Clinical Monitor if: (1) if one subject experiences a serious adverse event (SAE) assessed as possibly, probably, or definitely related to investigational product or (2) if there is a subject death assessed as possibly, probably, or definitely related to investigational product. Interpretation of adverse events that impact on halting rules will be done by the Clinical Monitor, Sponsor and IRB.

The clinical Monitor will review the safety data, after the first 50 vaccinations, and will present the data to the IRB board. In case of serious adverse events, vaccination will terminate immediately.

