13. ASSESSMENT OF SAFETY

Study staff will contact participants on day $3(\pm 2)$ and day $7(\pm 2)$ to ask about potential adverse effects or reactions participants might have developed after vaccination. This evaluation may be both face-to-face and virtual, especially considering that, due to the effects of the pandemic, face-to-face assistance could be affected. In addition, participants may report adverse events at any time to study personnel. Contact information will be provided at enrollment. Any adverse event will be investigated (Appendix O - INS Adverse Event Report Format) and participants will be referred to an independent physician for evaluation. The management and reporting of adverse events will be carried out taking into account the definitions and procedures detailed below.

13.1. Adverse events: definitions and procedures for recording, evaluating,

monitoring and reporting

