13.1.1. Definition of an adverse event (AE)

An AE is any event or situation that is detrimental to the health of the research subject, to whom an investigational product is being administered, and that does not necessarily have a causal relationship with its administration. Therefore, an adverse event (AE) can be any unfavorable and unintended sign; including an abnormal laboratory finding, symptom, or disease temporarily associated with the use of an investigational product; whether or not it is related to it. All AEs fall into one of two categories: "not serious" or "serious".

- A. Some examples of an AE include the following:
 - Any abnormal results in laboratory tests (hematology, clinical chemistry, or urinalysis) or other safety evaluations (eg, ECG, X-rays, vital sign measurements), including those that are worse from baseline, deemed clinically significant by the investigator's medical and scientific judgment (i.e. not related to a known comorbid condition).
 - Exacerbation of a chronic or intermittent pre-existing condition, including an increase in the frequency or intensity of the condition.
 - New conditions detected or diagnosed after administration of study vaccine, even though they may have been present before the start of the trial.
 - Signs, symptoms or the clinical sequela of a suspected drug interaction.
 - Signs, symptoms, or clinical sequela of a suspected overdose of study vaccine or a vaccine / concomitant drug.
 - An adverse effect of the study vaccine or a vaccine / concomitant drug.
 - An accident or injury.
- B. Events that DO NOT meet the definition of AE:
 - The medical or surgical procedures or other therapeutic interventions themselves are not AE, but the condition for which the surgery / intervention is required is an AE and must be documented accordingly.
 - The planned surgical measures and the condition (s) leading to these measures are not AE if the condition (s) was known prior to the observation period (see below) and it didn't get worse during the trial.

In the latter case, the condition should be reported as a medical history.

- Situations in which there was no detrimental medical event (eg, social and / or convenience income in a hospital).
- Predicted daily fluctuations of pre-existing disease (s) or condition (s) present or detected at the start of the trial that are not worsening.

Death is not considered an AE, but a result.

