13.1.2. Definition of a SAE

If an event is not an EA as defined above, then it cannot be an EAS, even if the seriousness conditions are met.

An SAE is defined as any detrimental medical event that, at any dose:

- Causes death.
- Is life threatening: The term "life threatening" in the definition of "serious" refers to an event in which a subject was at risk of dying at the time the event occurred. It does not refer to an event that hypothetically could have led to death if it had been more serious.
- Requires hospitalization or the extension of an existing hospitalization. In general, hospitalization means that the subject stayed (usually involving a stay of at least one night) in the hospital or emergency room for observation and / or for treatment that would not have been adequate in the doctor's office or in an outpatient setting. Complications that occur during hospitalization are EA. If a complication prolongs hospitalization or meets any other criteria for seriousness, it will be considered serious. If there are doubts as to whether there was a "hospitalization" or if it was necessary, the AE should be considered serious.

Hospitalization for scheduled treatment of a pre-existing condition that did not get worse from the start is not considered an AE.

• Causes a persistent disability / incapacity: The term disability means a significant impairment in a person's ability to perform normal life activities.

This definition does not seek to include experiences of relatively minor medical relevance, such as uncomplicated headache, nausea, vomiting, diarrhea, flu, and accidental trauma (for example, sprained ankle) that could hinder or prevent daily activities. , but not a significant disorder.

- It is a congenital anomaly / It is a congenital anomaly / congenital malformation in the subject's offspring.
- It is a significant medical event: Medical or scientific judgment should be used when deciding whether a SAE report is appropriate in other situations, such as major medical events that may not pose an immediate risk to life or result in death or hospitalization, but which may endanger the subject or may require medical or surgical intervention to avoid one of the other outcomes described in the definition above. In general, these events should be considered serious.

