13.1.3. Assessment of intensity and causality

A. Intensity evaluation:

The investigator will assess the intensity of each AE and SAE reported during the trial and assign it to one of the following categories.

- Absent (grade 0): no AE
- Mild (grade 1): an event easily tolerated by the subject, causing minimal discomfort and not interfering with daily activities.
- Severe (grade 3): an event that prevents normal daily activities. An AE that is assessed as severe should not be confused with an EAS. Severe is a category used to rate the intensity of an event; and both AE and SAE can be classified as serious.
- B. Causality Assessment

The investigator is obliged to evaluate the relationship between the study vaccine and each incidence of each AE / SAE. Causation will be determined as follows:

- **Related**: there is a reasonable causal relationship between study vaccine and AD.
- Unrelated: there is no reasonable causal relationship between study vaccine and AD.

A "reasonable possibility" of a relationship implies that there are facts, evidence, and / or arguments that suggest a causal relationship, rather than a relationship that cannot be ruled out.

The investigator will use clinical judgment to determine the relationship. Alternative causes, such as underlying disease (s), concomitant therapy or vaccine, and other risk factors, as well as the temporal relationship of the event to administration of the study vaccine, will be considered and investigated.

The investigator will also consult the Investigator's Manual in their assessment.

For each AE / SAE, the investigator **should** document in the medical record that he / she has reviewed the AE / SAE and provided an assessment of causation.

There may be situations where an EAS has occurred and the investigator has minimal information to include in the initial report for the sponsor. However, it is very important that the investigator always performs an assessment of the causality of each event prior to the initial transmission of the EAS data to the sponsor.

Investigator can change their opinion on causation based on follow-up information and submit SAE follow-up report with updated causation assessment.

Assessment of causality is one of the criteria used in determining regulatory reporting requirements.

All symptoms described by the patient at the express request of the local investigator are considered related to vaccination.

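### Section 10.11 gives two conflicting stopping rules: a halt for review after a related SAE or death, and immediate termination of vaccination for serious adverse events with no relatedness condition

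*Combined protocol and SAP*

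**What the plan says.** Section 10.11 of the combined protocol and SAP has two short paragraphs.

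- **Paragraph one** halts the study for safety review by the Clinical Monitor on either of two triggers. The first is "if one subject experiences a serious adverse event (SAE) assessed as possibly, probably, or definitely related to investigational product". The second is a death meeting the same relatedness condition. It adds: "Interpretation of adverse events that impact on halting rules will be done by the Clinical Monitor, Sponsor and IRB".
- **Paragraph two** provides for a Clinical Monitor review of safety data after the first 50 vaccinations, presented to the IRB. It ends: "In case of serious adverse events, vaccination will terminate immediately".

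The definitions that give these sentences their meaning are in section 13. Under 13.1.1 an adverse event is one "that does not necessarily have a causal relationship with its administration". Under 13.1.2 an adverse event becomes an SAE through its outcome or seriousness; one criterion is "Requires hospitalization or the extension of an existing hospitalization". Causality is a separate rating, made by the investigator under 13.1.3.

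Two other places mention stopping. Section 10.10 says that CDC, NAMRU6 or the IRB may terminate the trial. Section 17 says that the IRB and the Peruvian INS are notified if a safety issue would halt the study. Neither says how the two sentences in 10.11 relate to each other.

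**The concern.** A halting rule should settle in advance what happens when an event occurs. Here the two sentences differ in trigger (an SAE or death judged related, against serious adverse events without qualification) and in action (halt for review, against immediate termination). For an unrelated SAE they give opposite instructions.

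At stake is whether vaccination could end short of the planned maximum of 800 participants (section 10.4) over an event unrelated to the vaccine. Failing that, the Clinical Monitor, Sponsor and IRB would have to choose between two written rules while two sites are still vaccinating.

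**Working it through.** The plan gives no figure to reproduce. The check is to take each kind of event and read off what each sentence requires.

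| Event | Paragraph one of 10.11 | Last sentence of 10.11, read literally |
|---|---|---|
| SAE judged related, before the last vaccination | Study halted for review | Vaccination terminates |
| Death judged related, before the last vaccination | Study halted for review | Vaccination terminates (causing death is an SAE criterion in 13.1.2) |
| SAE or death judged unrelated, before the last vaccination | No action | Vaccination terminates |
| Any SAE after the last vaccination | Halt for review if related | No effect: no vaccination remains |

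**Step 1: can an unrelated event be an SAE?** Yes. 13.1.1 does not require a causal link, and 13.1.2 adds only seriousness. Accidents and injuries are among the adverse event examples in 13.1.1, so a hospital admission after an accident qualifies. The third row is therefore not empty.

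**Step 2: do the two sentences agree where both apply?** In part. In the first two rows dosing stops under either. They differ on whether the stop is a pause pending review or an end, and neither states how vaccination would resume.

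**Step 3: when can the conflict bite?** Each participant receives a single dose (section 2), and follow-up runs to days 180-200 (section 3). Only SAEs arising before the last participant is vaccinated can stop vaccination.

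**Step 4: how differently would the two triggers fire?** The documents give no SAE rate, so this is an illustration on assumed values. Let p be the all-cause SAE risk per participant over follow-up, and f the share of SAEs judged related. With n = 800:

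- P(at least one SAE) = 1 − (1 − p)^800
- P(at least one related SAE) = 1 − (1 − pf)^800

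| Assumed p | Any SAE | Related, f = 2% | Related, f = 5% | Related, f = 10% |
|---|---|---|---|---|
| 0.5% | 0.982 | 0.077 | 0.181 | 0.330 |
| 1% | >0.99 | 0.148 | 0.330 | 0.551 |
| 2% | >0.99 | 0.274 | 0.551 | 0.798 |

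At p = 0.1% the any-SAE figure is 0.551. By Step 3, all these values overstate how often vaccination would be stopped, because they count SAEs over the whole of follow-up. They show only that an any-SAE trigger and a related-SAE trigger are different rules in practice. They do not estimate the chance of a stop in this trial.

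**The case against.** The strongest defence is that there is really one rule. The last sentence closes a short section whose only SAE triggers are related events, and it directly follows the 50-vaccination review. It is natural to read its serious adverse events as those just described, or as those found at that review. For a related SAE, stopping dosing at once while a review proceeds is a coherent sequence. Named parties interpret adverse events for the halting rules. The literal text is the conservative one, and it may be deliberate, since section 12 says that FLUAD Quad is not authorized in Peru.

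Much of this stands. A narrower intention is plausible, the related-SAE case is close to consistent, and whether to stop on any SAE is the sponsor's choice. But no section states the narrower scope, and interpreting events does not tell those parties which written rule to apply. The unrelated-SAE case remains a direct contradiction.

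A reader might infer three stronger points, which the documents do not support.

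- **That the trial is underpowered because of this.** The wording changes neither sample size nor alpha. Power computed at some assumed early stop would show the cost of any early stop for any reason, not the size of this defect.
- **That participants are exposed to added danger.** Followed literally, the text stops sooner, and SAEs must reach the sponsor within 24 hours (13.1.4 and 13.1.7).
- **That the causality scales contradict each other.** Section 10.11 uses three levels of relatedness, while 13.1.3 uses Related and Unrelated. The 13.1.3 threshold asks for "arguments that suggest a causal relationship, rather than a relationship that cannot be ruled out", and no explicit mapping is given. Yet the same sentence speaks of a reasonable possibility, which suggests that possibly related belongs under Related. Section 13 also says "Any adverse event will be investigated (Appendix O - INS Adverse Event Report Format"; that form is not shown and may carry a graded scale. This is missing detail, not a contradiction.

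**Conclusion.** Section 10.11 is wrong as written. It states two stopping rules that give opposite instructions for an unrelated SAE occurring before the last vaccination, and that differ between pause and termination for a related one. The conclusion rests on the literal text of 10.11, read with the definitions in 13.1.1 and 13.1.2. It does not depend on any assumed rate.

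Its size cannot be put as a number, because the documents give no SAE rate and no probability of a stop. The consequence is a possible unwarranted end to vaccination, and an unsettled rule during dosing. The direct safety risk is limited. It should be fixed because the contradiction is in a decision rule and the remedy is cheap.

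**What to change.** Replace the last sentence of 10.11 with a single rule, for example:

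> After any SAE or death assessed by the investigator or the Clinical Monitor as possibly, probably or definitely related, vaccination pauses immediately at both sites. It resumes only after review by the Clinical Monitor, Sponsor and IRB. SAEs assessed as unrelated are reported under 13.1.7 and do not by themselves stop vaccination.

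This settles the trigger, whose assessment counts, the action and the route back to dosing. If the sponsor does intend to stop on any SAE, it should instead remove the relatedness condition from paragraph one and state whether the stop is a pause or a termination.

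An optional clarification is one sentence in 13.1.3 saying that possibly related counts as Related for the halting rule.

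The cost is a wording amendment with no new procedures. The first option gives up a literal any-SAE stop, which the sponsor should do knowingly. The optional sentence could lead to an extra pause for review. Whether Appendix O would need a matching change cannot be judged, because the form is not shown.
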